9 OVERALL STUDY DESIGN

9.1 Study design

Single centre, first-in-human pilot study of a novel medical device. The study will involve two groups up to 15 participants under controlled conditions. Of the 15 total participants, five (5) will be individuals who require a stent as a standard part of their urological procedure (Group 1) and 5-10 participants will be individuals who present to the ED-SSU with acute renal colic from a kidney stone and require a ureteric stent insertion (Group 2).

- Participants requiring a stent as part of standard urological procedure will be placed under general anaesthetic

in the operating room as per standard of care. The ureteric stent will then be inserted using the JSI under standard controlled conditions.

- In participants who present to the emergency room, a stent will be inserted in the ED-SSU cubicle using the JSI by an experienced urological doctor who is skilled in inserting ureteric stents. Analgesia for the procedure will include the local topical anaesthetic gel (i.e. Instillagel®) injected into the urethra prior to device insertion and a Pentrox “green whistle” temporary inhaled anaesthetic. A post-stent insertion KUB X-ray will then be performed to confirm position of the stent.

9.2 Schedule of Assessment

| Assessments | Screening (Day -7 to Day 1) | Procedure (Day 1) | Follow Up Visit (14 to 21 Days Post Tx) |
|------------------------------|--------------------------------|----------------------|--|
| Informed consent | X | | |
| Inclusion/Exclusion Criteria | X | | |
| Medical History | X | | |
| Demographics | X | | |
| CT Scan / MRI | X ^a | | |
| KUB X-Ray | | X ^b | |
| Renal Ultrasound | | (X) ^c | |
| User Questionnaire | | X ^d | |
| Participant Questionnaire | | X ^e | X |
| Device Deficiencies | | X | |
| Adverse Events | X | X | X |
| Concomitant Medications | X | X | X |
| Stone Management | | | X ^f |

- a. Prior imaging may be collected up to 30 days prior to treatment
- b. Performed after stent insertion for confirmation of position of the stent.
- c. If unable to confirm stent positioning via X-Ray, then proceed to perform renal ultrasound
- d. Performed ‘Immediately after stent-insertion’
- e. Performed ‘Prior Insertion’ and ‘Post Insertion’
- f. As per standard practice

9.3 Informed Consent

Potential participants will be informed of the risks and requirements of the study, and during the study, participants will be given any new information that may affect their decision to continue participation. They will be told that their consent to participate in the study is voluntary and may be withdrawn at any time with no reason given and without penalty or loss of benefits to which they would otherwise be entitled. Only participants who are fully able to understand the risks, benefits and potential AEs of the study, and provide their consent voluntarily will be enrolled. Participants must sign an informed consent form (ICF). Where a subject is unable give informed consent, they will not be considered for inclusion in the study.

9.4 Inclusion criteria

1. Consenting adult participant male or female, age \geq 18 years old.
2. Participant about to undergo stent insertion as part of their routine urological care or
3. Patient who has presented to the emergency department with acute renal colic requiring admission to hospital for a ureteric stent.
4. Ability to provide informed consent by study participant.
5. Willingness and ability to comply with study-related procedures/assessments.

9.5 Exclusion criteria

1. Age <18.
2. Known allergy to local anaesthetic lubricating gel, Pentrox “green whistle” inhaler anaesthetic.
3. Stone larger than 1cm.
4. Stone impacted in ureter.
5. Men with prostate larger than 100cc in size.
6. Participant with severe sepsis requiring nephrostomy or stabilisation in an operating room.

9.6 Representativeness of included population

The investigation population represents the intended target population in terms of age (adult population) and gender (any gender). Subjects about to undergo stent insertion as part of their routine urological care or have presented to the emergency department-short stay unit with acute renal colic requiring admission to hospital for a ureteric stent will be treated with the JSI. Therefore, the included population is considered a representative sample for the intended use of JSI.

9.7 Definition of enrolment

Time at which, following recruitment and before any clinical investigation-related procedures are undertaken, a participant who meets the eligibility criteria signs and dates the informed consent form.

9.8 End of treatment

The end of treatment is defined as the day the decision was made to permanently discontinue all study treatment and participant engagement. End of treatment is the date of final participant survey completion and definitive stone

management surgery (14-21 days post enrolment). Each participant will be followed through to the end of treatment, unless he/she has died or withdrawn consent, or the study is terminated.

9.9 Follow up phase

Participants will attend one follow-up visit which will occur approx. 14 to 21 days post-stent insertion with JiffyStent Inserter.

The following assessments will be performed:

- Completion of participant survey
- Definitive stone management surgery (Standard of Care)
- Recording adverse events (via medical record review and participant assessment)

Ongoing standard of care medical evaluation/follow up will continue at the site following final trial visit and follow up.

9.10 End of study

The clinical investigation will be considered complete six (6) months after the last participant is enrolled in the study.

9.11 Activities by sponsor representatives

Procedures related to the clinical investigation will be performed by the principal investigator, study coordinators, and/or other authorised study staff, as applicable. A sponsor representative may be present during investigational procedures for technical support.

The following activities are performed by the Sponsor and/or its representative:

- Provision of instructional advice regarding JSI set up, procedure, use and disposal.
- The sponsor and/or its representative will provide technical support only and will not physically partake in device use or implementation.
- Participants will be consulted, and verbal consent obtained prior to sponsor and/or its representative entering participant and treatment location.

9.12 Potential confounding factors

Potential confounding factors that may compromise the outcome of the clinical investigation include:

- Misuse of the device by the investigator.
- Miscalculation of the eligibility criteria by the investigator.
- Miscalculation of SAE in relation to the device by the investigator.

As to minimise these potential confounding factors, appropriate control measures are implemented by design and with the investigators before the study start and carefully monitored throughout the study.

9.13 Monitoring plan

Avania (Contract Research Organization (CRO)) has designed and implemented a comprehensive monitoring plan. This plan is essential to ensure that the trial adheres to ethical and regulatory standards, maintains data integrity, and ultimately generates reliable results. The CRO will perform a risk assessment to identify potential challenges and risks associated with the trial. Based on this assessment, Avania has designed a monitoring strategy that includes the frequency and type of site visits. In a pilot trial, close monitoring is essential to evaluate the trial's feasibility, identify operational issues, and ensure participant safety. The CRO's monitoring team will conduct both remote and on-site visits to assess source data verification, informed consent processes, and compliance with the study protocol. The CRO will ensure proper documentation, data accuracy, and timely query resolution. The CRO will outline the qualifications and responsibilities of the monitors, as well as the communication and reporting mechanisms to keep all stakeholders informed of trial progress.

10 ETHICS

10.1 Guiding Principles

This study is to be performed in accordance with the ethical principles of the Declaration of Helsinki (June 1964 and amended 1975, 1983, 1989, 1996, 2000, 2008 and Note of Clarification 2002 and 2004), ICH GCP Notes for Guidance on Good Clinical Practice (CPMP/ICH/135/95) annotated with Therapeutic Goods Administration comments, NHMRC National Statement on Ethical Conduct in Research Involving Humans 2007 (Updated 2018) and ICH GCP Notes for Guidance on Good Clinical Practice (CPMP/ICH/135/95).

10.2 Ethical considerations of recruitment

All potential participants in this study will be adults over 18 years of age, sound of mind, and able to be fully informed of the requirements and risks of the study. Participants presenting to the ED-SSU unit may be experiencing pain and the hope of having this pain relieved immediately might limit their ability to comprehend the risks, although they be minimal, involved in taking part in this study. Doctors in urology are skilled at managing patients under extreme stress such as those suffering renal colic or prior to surgery. Careful consideration will be given to ensuring that patients understand that their immediate pain relief is of utmost importance and not related to their participation in the study.

10.3 Ethical considerations of consent

The ethical considerations related to consent will be minimal in this project. This is primarily because eligible participants all require a ureteric stent. This stent can be inserted with the JSI or by the standard procedure in an operating room. Therefore, the consent is no different to the usual consent process for having a stent inserted apart from the fact that this is a new technique with a novel medical device. Only fully informed participant who can understand English or have it carefully explained to them by an interpreter we be eligible to participate in the study. There are no cultural issues that may affect this consent process.

10.4 Management of participant's expectation of the perceived benefit of participating in the research

Participants expectations will be managed by a careful and adequate fully informed consent process. This will involve explaining to the participant that the JSI is currently an experimental medical device. They will be informed that the insertion of a correctly placed stent is identical to that achieved by the standard procedure in an operating room. It will also be explained that we expect there to be a 5 to 10% failure rate that will require going to theatre for insertion of a stent via the standard procedure. It will also be carefully explained that there is a risk of incorrect placement and potential damage to the ureter that maybe more easily recognised in the operating room with the benefit of real-time image intensifier X-ray.

10.5 Ethical considerations relating to the collection and/or use of the information/data in this project

Participants will be allocated a unique study number. The site research coordinator will compile an enrolment log, including the participant's name, date of birth, hospital identification number, unique study number and date and time of procedure. Subsequent data will be identified by the unique study number only. The enrolment log and study data will be kept separately. Study data will be entered into a password protected REDCap database managed by the principal investigator. No identifying data will be entered into the database.

Similarly, hard copies of study data collected on paper source worksheets will be stored separately in the locked office of the principal investigator. Only the PI and research team will have access to this information, and they will not disclose this information to any other person or entity.

When archiving, the study site investigator will take all appropriate measures to safeguard and prevent access to this data by any unauthorised third party.

The investigator will maintain the confidentiality of all study documentation and take measures to prevent accidental or premature destruction of these documents. The investigator will retain the study documents at least 15 years after

the completion or discontinuation of the study. The investigator must notify the study management committee prior to destroying any essential study documents following the study completion or discontinuation.

If any investigator retires, relocates, or otherwise withdraws from conducting a study, the responsibility for maintaining records may be transferred to the coordinating centre or another investigator. The coordinating centre must be notified of and agree to the change. All associated documentation must also be updated.

Austin Health medical records will be approached to allow the investigators access to electronic medical records of participants. We aim to have this permission granted as soon as possible. Medical records will be accessed to collect data regarding the participant's previous medical treatments in Austin Health.

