7.3 Evaluation of clinical data

As this clinical investigation is a first-in-human, feasibility study there is no clinical data for evaluation.

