11.2.1 Clinical risks

| Hazard | Risk | Mitigation and residual risk |
|--|--|--|
| 
Guidewire perforates the ureter which is unrecognised while using the device.
 
Probability: Likely Severity: Serious See Appendix A for scores at bottom of sheet
 | 
The stent will be inserted outside of the ureter. Consequences: Obstruction not relieved Pain not relieved Increased risk of infection Risk of long-term ureteric stricture The risk of a 1.67 millimetre diameter hole in the ureter is minimal. There is a small risk of long-term ureteric stricture which may be related to the perforation or more likely the impacted stone causing inflammation and scarring at this point in the ureter. Despite optimal conditions, this can sometimes happen during the standard procedure in an operating room but may be recognised with the benefit of the in-theatre imaging intensifier X ray machine.
 | 
A post-stent insertion KUB X-ray will be performed to confirm position of stent. Patients with incorrectly placed stents will be taken to the operating room for removal of the stent and insertion of a new stent under image intensifier guidance.
 |
| 
Guidewire does a U-turn in the ureter
 
Probability: Possible Severity: minor
 | 
The stent will be in the ureter below the level of obstruction. Consequences: Obstruction not relieved Pain not relieved This will cause no permanent harm to the participant.
 | 
A post-stent insertion KUB X-ray will be performed to confirm position of stent. This risk can be mitigated by careful participant selection as per our indications of a stone <1cm in size and in stones that are not impacted. Participants with incorrectly placed stents will be taken to the operating room for removal of the stent and insertion of a new stent under image intensifier guidance.
 |

| | | |
|---|--|---|

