Appendix A: Risk Score Matrix

| Probability Scorings: | | |
|-----------------------|------|-------|
| No. | Harm | Value |
| Almost Certain | 100% | 5 |
| Likely | 10% | 4 |
| Possible | 1% | 3 |

| | | |
|----------|-------|---|
| Unlikely | 0.10% | 2 |
| Rare | 0.01% | 1 |

| Severity: | | |
|--------------|---|-------|
| Rating | Definition | Value |
| Catastrophic | Results in death | 5 |
| Critical | Results in permanent impairment or life-threatening injury | 4 |
| Serious | Results in injury or impairment requiring professional medical intervention | 3 |
| Minor | Results in temporary injury or impairment not requiring professional medical intervention | 2 |
| Negligible | Inconvenience or temporary discomfort | 1 |

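### The 5-10% failure rate to be given at consent is not reconciled with the risk table, which scores unrecognised ureteric perforation alone at 10% and lists at least nine other hazards that end in theatre

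*Protocol*

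**What the plan says.** Section 10.4 of the protocol, on managing participants' expectations, states: "It will also be explained that we expect there to be a 5 to 10% failure rate that will require going to theatre". No derivation is given. The next sentence of 10.4 says that incorrect placement and possible damage to the ureter will also be explained, without saying whether these are part of the 5-10%.

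The clinical risk table in section 11.2.1 has the row "Guidewire perforates the ureter which is unrecognised while using the device. Probability: Likely Severity: Serious". Its stated consequence is a stent lying outside the ureter. Its mitigation is an X-ray after insertion, followed by: "Patients with incorrectly placed stents will be taken to the operating room for removal of the stent". The row refers to Appendix A for its scores. Appendix A gives each probability label one value: Almost Certain 100%, Likely 10%, Possible 1%, Unlikely 0.10%, Rare 0.01%.

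Section 7.3 says that "there is no clinical data for evaluation". Section 10.2 says that the hope of immediate pain relief "might limit their ability to comprehend the risks, although they be minimal".

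**The concern.** The failure rate in 10.4 and the scores in 11.2 describe overlapping events, yet nothing in the protocol connects them. A total of 5-10% leaves little or no room for any other failure once a single hazard is scored at 10%, and the tables list many others with the same end point.

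The figure matters because it is to be given to participants before they agree to a first-in-human device. Those in Group 2 present to the emergency department with acute renal colic, and section 10.2 itself recognises that pain may limit how well they take in the risks. The same section calls the risks minimal, while the table scores perforation Likely/Serious and pain or discomfort Almost Certain/Serious. Appendix A defines Serious as needing professional medical intervention.

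**Working it through.** **The plan's own figure.** The 5-10% cannot be reproduced, because 10.4 shows no calculation or source. The check is therefore to rebuild a rate from section 11.2 and Appendix A.

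**Inputs, with Appendix A values read as point probabilities**

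- Unrecognised perforation (11.2.1), Likely: 0.10.
- Eight hazards scored Possible whose listed outcome is theatre, 0.01 each: guidewire U-turn (11.2.1); spool jam or device failure with no stent, spool jam with partial insertion, and guidewire set too short (11.2.2); Wi-Fi will not connect, Wi-Fi disconnects, inserter battery runs out, and LED failure (11.2.3).
- One hazard scored Unlikely, ureteric orifice not seen (11.2.1): 0.001.
- Five hazards scored Possible where a replacement or theatre is offered, 0.01 each (11.2.3): camera, electronic board, battery fault, smart-device battery, and image quality.

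A guidewire set too long (11.2.2) is left out, because a misplaced stent is described there as very rare.

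**Formulas.** Independent hazards: 1 − ∏(1 − pᵢ). Mutually exclusive hazards: Σpᵢ.

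**Results**

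1. Perforation alone: 10.0%, equal to the upper end of 5-10%.
2. Perforation, U-turn and too-short guidewire: 1 − 0.90 × 0.99² = 11.8% (sum 12.0%).
3. All ten theatre-only hazards: 1 − 0.90 × 0.99⁸ × 0.999 = 17.0% (sum 0.10 + 0.08 + 0.001 = 18.1%).
4. Adding the five replace-or-theatre hazards: 1 − 0.90 × 0.99¹³ × 0.999 = 21.1% (sum 23.1%).

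**What would make 5-10% fit**

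- *Perforation and misplacement excluded.* Dropping perforation, U-turn and too-short guidewire leaves 1 − 0.99⁶ × 0.999 = 5.9%, or 1 − 0.99¹¹ × 0.999 = 10.6% with the replace-or-theatre hazards.
- *A lower perforation score.* For the theatre-only set to total 10%, perforation can be at most 1 − 0.90 / (0.99⁸ × 0.999) = 2.4%.
- *Scores as upper limits of tenfold bands.* The lower limits give 1 − 0.99 × 0.999⁸ × 0.9999 = 1.8% (2.3% with the extra five). Geometric midpoints give 5.6% (7.1%). The band then runs from about 2% to 17% (21%) and contains 5-10%.

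**Scale.** Going to theatre applies literally to Group 2, because Group 1 is already in the operating room (section 9.1). With the maximum of 10 Group 2 participants, 5-10% means 0.5-1.0 expected failures, against 10 × 0.170 = 1.7 under the point reading.

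**The case against.** The best defence is that Appendix A is a risk-scoring scale and not a set of estimates. Its steps are tenfold, and Almost Certain is set at 100%, which suggests orders of magnitude. Read as bands, the scores are compatible with 5-10%. This stands as a possible reading, but Appendix A prints single values and does not call them bands.

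Section 10.4 also mentions incorrect placement and ureteric damage separately, straight after the failure rate. If the 5-10% means only failure to insert a stent, the table gives about 6-11%, close to what is stated. This is a serious point. Against it, 10.4 describes the figure as failures that require theatre, and 11.2.1 sends misplaced stents there. The text does not settle which is meant.

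The hazards are not cleanly separate either. Device failure or spool jam reads as a catch-all, board faults could cause Wi-Fi, LED or camera failure, and the two inserter-battery rows may overlap. Overlap lowers the total. However, it falls to 10% only if every other hazard coincides with perforation, and a Wi-Fi failure before the procedure starts cannot.

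The table does not say whether scores are before or after mitigation. For the U-turn, participant selection could lower the probability. For perforation, the listed X-ray detects the event but does not prevent it.

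On the word minimal, the perforation row itself calls the risk from the small hole minimal, so 10.2 may be speaking of consequences. That does not fit well with a severity score of Serious in the same row.

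Two stronger inferences are tempting. A reader might conclude that participants are told about half the true failure rate. The documents do not support this: no true rate is known, and 17-21% appears nowhere in the protocol. A reader might also treat 5-10% as the benchmark for the safety committee. Section 10.4 makes no such link, and section 15.8 leaves the committee's activities to a charter that is not shown.

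**Conclusion.** The inconsistency is real but limited. Perforation at 10% does not by itself contradict a range that ends at 10%. The conflict arises because at least nine other listed hazards also end in theatre. With Appendix A values as point probabilities, the theatre-only hazards total about 17% (independent) or 18% (mutually exclusive), and about 21-23% if all five replace-or-theatre hazards are added. These totals depend on the point reading, on limited overlap between hazards, and on the scores applying to the device as used.

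The 5-10% can be right under any of three conditions: misplacement is excluded, perforation is much rarer than scored, or the scores are upper limits. The protocol states none of them. The documents do not show which of the two figures is correct. They do show that the number for consent has no stated definition or basis and does not agree with the risk table on a plain reading. It should be corrected before consent relies on it, but it does not affect the design or the planned analysis.

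**What to change.** Reconcile section 10.4 with section 11.2 and Appendix A, by either re-scoring perforation and giving the basis for the score, or revising the 5-10%. In Appendix A, say whether the values are point estimates or upper limits, and whether scores are before or after mitigation.

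In 10.4 and the consent information, state whether the failure figure includes misplaced stents and perforation, what it is based on, and that the rate in humans is unknown, in line with section 7.3. Make clear that the statement about going to theatre concerns Group 2. Bring the word minimal in 10.2 into line with the Likely/Serious and Almost Certain/Serious scores.

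Do not insert 17-21% as the expected rate. It is a derived illustration that depends on how an ordinal scale is read.

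The cost is a change to protocol and consent wording. The expectation given to participants may become less favourable.
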